##### **Study design:**

The study will take place over a period of 27 months. The recruitment phase will last approximately 24 months and each patient will participate for approximately 3 months.

At the inclusion visit (D0), the investigator will ask the patient whether he would like to participate in the study and will obtain his written consent. Refusal to participate including the reason if available will be collected in a register specific to this study (study register). The collected data will allow any selection bias to be identified.

Each patient agreeing to participate in the study will be randomised by receiving a randomisation number and assigned to its corresponding group. Randomisation will be done by envelopes (See Section 7.5). The investigators or medical team will send a randomisation fax to Patientys for each patient included in the study. Patientys will forward the anonymised data to the contract research organisation (CRO) in charge of the data monitoring.

The randomisation will follow a 3:1 ratio and the patients will be included in one of the following 2 groups:

- Group without 'remote additional personalised nurse-led follow-up': patients will receive the healthcare given routinely by their medical team (100 patients).

OR

- Group with 'remote additional personalised nurse-led follow-up': patients will receive telephone calls from a nurse in addition to the healthcare given routinely by their medical team (300 patients).

All the patients will be seen according to normal practice by the study medical team. In this study, 3 data collection time-points at monthly intervals are defined (D30, D60, D90); however the frequency of visits should not be adjusted and the medical team should maintain his routine practice (example: if the investigator is used to see the patient on D15, the visit will still take place, but no information, except pharmacovigilance data, will be collected). As

such, the data from the closest defined visit will be reported in the case report form (CRF) at each time point (see Figure 1).

During the inclusion consultation, the medical team will provide the patient with a patient diary with all the main information regarding its treatment and in which he should report some information (see Section 6.2).

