The telephone calls will be made by a nurse from a company specialised in patients support called Patientys. Patients in the group with 'remote additional personalised nurse-led follow-up' will be contacted 8 times during the study (at D1, D7, D14, D21, D28, D44, D59 and D89, see Figure 1). The nurse will make sure that the treatment takes place in good conditions; she cannot intervene in the medical care of the patient, nor give answer to the questions relative to the disease or to the treatment of the patient. The medical team remains the privileged contact of the patient.

During the informed consent process, the patient may authorize a relative (i.e. a person he trusts and who can be among other, a family member, a friend or a housemate) to assist him during the nurse-led phone call. The first and last name of this person will be specified on the informed consent form.

During the first telephone call at D1, the nurse will confirm the enrolment of the patient in the study and will re-explain the calls schedule. Following this call, if the patient agrees to give the contact details of their physician and pharmacist, then the nurse will inform them, by letter or phone call, of the patient participation in the study.

During the following telephone calls, the nurse will perform a clinical evaluation by using a pre-established questionnaire and will collect treatment related AEs (see Section 6.2.3) as well as the pharmacovigilance (PV) information. After each telephone call, the nurse will establish a report.

The telephone call reports will be sent to the investigators on the same day of the nurse follow-up phone call.

The investigator will verify the severity of the AE and will determine the causal relationship with the oral targeted therapy.

- If case of serious adverse event (SAE), the investigator must complete and send immediately the serious adverse event (SAE) form (SAE form) to the CRO in charge of data monitoring (within 24h of the event). The causality will be determined by the investigator and recorded on SAE declaration form. In case of treatment exposure during pregnancy please refer to Section 5.3.2.2.
- In case of non-serious AE and/or of any other PV information, the investigator should complete and send the AEs page of the CRF to the CRO in charge of data monitoring within 7 days of the event. The causality will be determined by the investigator and recorded on the AEs page of the CRF.

[figure not shown]

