#### **5.3.2 Assessment of adverse events**

The AEs will be collected by the medical team during patient consultation or by the nurse of the specialised call centre Patientys during the follow-up phone call.

The nurse will transmit to the investigator the telephone call report by e-mail or by FAX on the day of the follow-up phone call and will provide [REDACTED] with the AE page(s) of the CRF, if applicable. If needed the nurse may contact the medical team. The investigator will check, confirm, and comment the AEs reported by the nurse. [REDACTED] will add any relevant event. [REDACTED] will also complete the AEs page of the CRF sent by the nurse by adding the intensity and the causal relationship with the oral targeted therapy.

Each AE will be recorded in the CRF and send to the CRO in charge of the data monitoring. The modalities of transmission to the CRO in charge of data monitoring and to the sponsor of the study are described in Sections 3.1, 6.2.3 and 8.4.

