### **6.2.2 Other visits (MV1, MV2, MV3)**

At the 2nd and 3rd consultation visits (D30 and D60) during which data will be collected, the patient will be asked to:

- Complete the compliance questionnaire (Girerd).
- Complete the quality of life questionnaire (FACT Lung; only on D30).
- Bring their oral targeted therapy packets (empty or started) prescribed/consumed since the previous consultation visit.

- Bring their patient diary.

All the questionnaires will be completed before the start of consultations, in the doctor's office or any other available private place.

The medical team will record the number of tablets taken and not taken, and will report this information in the patient's CRF.

Adverse events and concomitant diseases and medications will be collected during these consultations. Data on the utilization of healthcare services (hospitalizations, emergency room visits, unscheduled consultation visits), including the number of visits and the number of calls to the general practitioner, will also be collected using the information reported by the patient in their patient diary.

During the last consultation visit (MV3 on D90), the patient will be asked to:

- Complete the compliance questionnaire (Girerd),
- Complete the quality of life questionnaire (FACT Lung),
- Complete the global satisfaction questionnaire,
- Bring their oral targeted therapy packets (empty or started) prescribed/consumed since the previous consultation visit,
- Bring their patient diary.

All the questionnaires will be completed before the start of consultations, in the doctor's office or any other available private place.

The medical team will record the number of tablets taken and not taken, and will report this information in the patient's CRF.

Adverse events and concomitant diseases and medications will be collected during these consultations. Data on the utilization of healthcare services will also be collected using the information reported by the patient in their patient diary.

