### 6.2.3      **Remote additional nurse-led follow-up**

This follow-up will be implemented only for patients in the 'with nurse-led follow-up' group. During each telephone call, the nurse will have to complete a pre-established questionnaire, an AE page, and a SAEs declaration form.

During the informed consent process, the patient may authorize a relative (i.e. a person he trusts and who can be among other, a family member, a friend or a housemate) to assist him

during the nurse-led phone call. The first and last name of this person will be specified on the informed consent form.

During the first telephone call (D1), nurses will confirm the registration of the patient. The name and contact details of the general practitioner and pharmacist of the patient will be collected in a study registry. These data will allow to inform the general practitioners and pharmacists of patients included in the ‘with remote additional personalised nurse-led follow-up’ group of the patient's participation in the study and to send them the global satisfaction questionnaire at the end of the study.

During subsequent telephone calls, the nurse will establish a ‘clinical evaluation’ using questions such as:

- “How are you feeling today?”
- “Did you take your medicine as your doctor has prescribed?”
- “Did you complete patient diary of the study?”

She will also collect AEs encountered during treatment intake. In particular, the following events will be collected:

- Gastrointestinal disorders (diarrhea, stomatitis, dyspepsia, cheilitis).
- Skin and subcutaneous tissue disorders (rash, acneiform dermatitis, pruritus, dry skin, the palmar-plantar syndrome).
- Infections (paronychia, cystitis).
- Appetite or metabolic disorders (decreased appetite, dehydration, hypokalemia).
- Nervous system disorders (dysgeusia).
- Eye disorders (conjunctivitis, dry eye, keratitis, tearing, light sensitivity).
- Respiratory disorders (epistaxis, rhinorrhea, interstitial lung disease, pneumonia, respiratory distress, allergic alveolitis).
- Musculoskeletal disorders (muscular spasms).
- General disorders (fever).
- Investigations (weight loss).
- Others.

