### 7.3.4 Safety analyses

Safety analyses will be performed on all patients who received at least one dose of oral targeted therapy during the 3-month follow-up. Only events considered related to oral targeted therapy will be considered in the statistical analysis.

For each study group, the number of patients with at least one of the following will be described:

- One AE related to the oral targeted therapy.

- One AE related to the oral targeted therapy of grade  $\geq 3$ .
- One SAE related to the oral targeted therapy.
- One AE related to the oral targeted therapy leading to a definitive discontinuation of the drug.
- One AE related to the oral targeted therapy leading to a temporary discontinuation of the drug.
- One AE related to the oral targeted therapy leading to a dose reduction.

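### AEs are actively collected at eight extra nurse calls in one arm only, so the planned all-source AE tables by arm are biased towards more AEs in the nurse arm

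*Combined protocol and SAP*

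**What the plan says.** The calls belong to one arm. Section 6.2.3 states: "This follow-up will be implemented only for patients in the 'with nurse-led follow-up' group". Section 3.1 fixes their number; these patients "will be contacted 8 times during the study (at D1, D7, D14, D21, D28, D44, D59 and D89").

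AE collection is part of every call: "During each telephone call, the nurse will have to complete a pre-established questionnaire, an AE page, and a SAEs declaration form" (Section 6.2.3). Tables 1 and 2 also mark AE collection at all eight. For the calls after D1, Section 6.2.3 adds: "She will also collect AEs encountered during treatment intake. In particular, the following events will be collected", followed by ten named categories and a residual one.

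Both arms share the medical visits. AE collection is marked at D0, D30, D60 and D90. For the follow-up visits Section 6.2.2 says only: "Adverse events and concomitant diseases and medications will be collected during these consultations". No event list is described for them. At routine visits outside these time points, "no information, except pharmacovigilance data, will be collected" (Section 3.1), again in both arms.

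The two sources feed one record. Section 5.3.2 says: "The AEs will be collected by the medical team during patient consultation or by the nurse of the specialised call centre". The investigator then confirms the nurse's entries and adds intensity and causality.

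Section 5.3.1 defines the safety endpoints as numbers of related AEs. Section 7.3.4 gives the presentation: "For each study group, the number of patients with at least one of the following will be described", restricted to related events. Neither section separates AEs by source or cautions about unequal collection.

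**The concern.** Safety is a secondary objective (Section 2.2.2), and the tables are laid out by randomised arm. When one arm is asked about AEs far more often, and with named prompts, a difference in recorded AEs mixes toxicity with detection. The Introduction itself expects the calls to help patients report AEs and nurses identify them, so higher ascertainment is part of how the intervention is meant to work.

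Two errors of reading are possible. A reader could take an excess of AEs in the nurse arm as harm when it is better reporting. Or, if earlier handling of symptoms truly reduces toxicity, the extra detection could cancel the reduction in the table and the benefit would be missed.

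**Working it through.** The plan gives no figure for AE detection, so there is none to reproduce. The collection points can be counted. The size can only be illustrated under stated assumptions.

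**1. Scheduled AE collection points (Tables 1 and 2)**
- Control arm: D0, D30, D60, D90 = 4.
- Nurse arm: 4 visits + 8 calls = 12.
- After baseline: 3 against 11.
- If the D1 call is treated as administrative, because the event list applies only to the later calls: 4 against 11.
- If there are k other routine visits in each arm, each supplying pharmacovigilance data, the comparison is (12 + k) to (4 + k). The documents do not fix k.

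**2. Event counts with no true difference**

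Assumptions (not in the documents): medical visits capture a fraction pv of AEs (0.5 to 0.8), the calls together capture a fraction pc (0.7 to 0.9), and the two are independent. The control arm records pv. The nurse arm records 1 − (1 − pv)(1 − pc).

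Ratio = [1 − (1 − pv)(1 − pc)] / pv

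- pv 0.5, pc 0.9: (1 − 0.5 × 0.1) / 0.5 = 0.95 / 0.5 = 1.90
- pv 0.5, pc 0.7: (1 − 0.5 × 0.3) / 0.5 = 0.85 / 0.5 = 1.70
- pv 0.8, pc 0.9: (1 − 0.2 × 0.1) / 0.8 = 0.98 / 0.8 = 1.23
- pv 0.8, pc 0.7: (1 − 0.2 × 0.3) / 0.8 = 0.94 / 0.8 = 1.18

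The range is about 1.2 to 1.9. If visits and calls caught the same events instead of being independent, the last case would give 1.0.

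**3. Patients with at least one AE, the quantity in Section 7.3.4**

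Further assumption: AEs per patient are Poisson with mean 3. The proportion with at least one recorded AE is 1 − exp(−3 × fraction captured).

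- pv 0.5, pc 0.9: nurse 1 − exp(−2.85) = 0.942; control 1 − exp(−1.50) = 0.777; ratio 1.21
- pv 0.8, pc 0.7: nurse 1 − exp(−2.82) = 0.940; control 1 − exp(−2.40) = 0.909; ratio 1.03

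The ratio shrinks because most patients already have at least one recorded event. This protection is weaker in rows with fewer events per patient.

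**4. Which events are most affected**

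Assume that onset is uniform over 90 days and that an AE is recorded only if a scheduled contact falls within w days of onset. The control gaps are 30, 30 and 30 days. The nurse-arm gaps are 1, 6, 7, 7, 7, 2, 14, 15, 1, 29 and 1 days. The fraction captured is the sum of min(gap, w) divided by 90.

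- w = 7: control 21/90 = 23%; nurse 53/90 = 59%
- w = 14: control 42/90 = 47%; nurse 74/90 = 82%
- w = 21: control 63/90 = 70%; nurse 82/90 = 91%
- w = 30: 100% in both arms

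Short-lived events are distorted most, and lasting ones little or not at all. Sections 3.1 and 6.1 differ on whether the sixth call is at D44 or D45; the two should be reconciled, but these results are the same with either.

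**5. Why the definition of source matters**

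If each AE were assigned to the source that recorded it first, and calls usually came first, visit AEs in the nurse arm would be pv(1 − pc). The ratio to control would be 1 − pc, that is 0.1 to 0.3 for pc of 0.9 to 0.7. That reverses the bias. Counting every AE reported at a visit, whether or not also reported at a call, gives pv/pv = 1.0 under the same independence assumption.

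**The case against.** A reader might infer that the nurse arm will look more toxic. The documents do not support that certainty. The direction of the detection bias is clear, but its size is unknown and a true reduction could offset it. Section 7.3.4 is descriptive, names no test and draws no conclusion about toxicity, and AEs are not among the variables listed for comparison in Section 7.3.3.

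A reader might also take 12 against 4 as the full contrast, or conclude that visits have no checklist. Other routine visits supply pharmacovigilance data in both arms, and all AEs from consent to D90 are reportable (Section 5.3.2.2). The CRF AE page is not in the documents, so one can say only that no visit checklist is described. Nor can the 1.9 be carried over to the Section 7.3.4 table, which counts patients and not events.

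The plan also has safeguards: the investigator confirms nurse-reported AEs, and only related events are analysed. These act on events already reported. They cannot recover events that control patients never mentioned, and the study is open-label.

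A further objection concerns remedy. Asking control patients the nurse's event list would equalise prompting, but would alter the routine care that serves as comparator and could dilute the primary contrast. This stands, and the fix avoids it.

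What remains is that collection is unequal by design, the sources are pooled, and nothing in the plan lets a reader separate them.

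**Conclusion.** The concern holds as a bias of known direction and unknown size. Followed as written, the plan gives an all-source comparison of related AEs tilted towards more AEs in the nurse arm, and a real reduction could be masked. Under the assumed capture rates and independence, the event-count ratio with no true difference is about 1.2 to 1.9. For patients with at least one AE it is about 1.03 to 1.21 if the mean is 3 AEs per patient. Greater overlap between visits and calls, or longer-lasting events, would bring these closer to 1. The bias is likely least for SAEs, which tend to surface without prompting, and smaller for grade ≥3 events than for milder ones. Rows for AEs leading to interruption or dose reduction are less secure, because same-day call reports reach the investigator who decides on treatment.

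The primary endpoint's definition and the sample size calculation do not depend on this point. The detailed SAP to which the protocol defers is not among the documents and might add an analysis by source. It would need source to be recorded at collection. The nurse's AE pages already reach the CRO separately, so source is partly traceable, but whether an AE was also reported at a visit is not provided for.

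**What to change.** - **AE page:** add two fields: reported at a nurse call (yes/no) and reported at a medical visit (yes/no), with both allowed. Do not define source as first recorded. State in the completion guidance that confirming a nurse's entry does not by itself count as a visit report.
- **Section 7.3.4:** keep the all-source table. Beside it, add a by-arm table of AEs reported at medical visits, whether or not also reported at a call. Show call-only AEs separately for the nurse arm. Treat the event counts of Section 5.3.1 in the same way.
- **Interpretation:** state in advance that all-source differences in non-serious AEs may reflect detection, and that any between-arm safety conclusion rests mainly on the SAE and grade ≥3 rows already planned.
- **Comparator:** do not add the nurse's event list to control-arm visits.

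The cost is one more CRF item (the two yes/no fields) and one table. Safety reporting, the primary analysis and the sample size are unchanged. The visit-based table reduces the bias but does not remove it: the calls at D28, D59 and D89 come one or two days before the visits, and their reports reach the investigator the same day, so visit reports in the nurse arm are themselves partly prompted.

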## 7. STATISTICAL METHODS AND DETERMINATION OF PATIENTS SAMPLE SIZE

### 7.1 STATISTICAL DESIGN

This is a routine clinical practice, randomised, open-label, multicentre, study.

Patients will be randomised in one of the following 2 groups:

- Group ‘without remote additional personalised nurse-led follow-up’: patients will receive the healthcare given routinely by the medical team (100 patients).
- Group with ‘remote additional personalised nurse-led follow-up’: patients will receive telephone calls from a nurse in addition to the healthcare given routinely by their medical team (300 patients).

### 7.2 NULL AND ALTERNATIVE HYPOTHESES

The null and alternative hypotheses are as follows:

$H_0$  : no difference exists between the average doses of the first 3-month oral targeted therapy between ‘with remote additional personalised nurse-led follow-up’ and ‘without remote additional personalised nurse-led follow-up’ groups.

$H_0$ : *average cumulated dose* ‘With nurse-led follow-up’ = *average cumulated dose* ‘Without nurse-led follow-up’

$H_1$  : a difference exists between the average doses of the first 3-month oral targeted therapy between ‘With nurse-led follow-up’ and ‘Without nurse-led follow-up’ groups.

$H_1$ : *average cumulated dose* ‘With nurse-led follow-up’ ≠ *average cumulated dose* ‘Without nurse-led follow-up’

### **7.3.1 Demographic information and baseline characteristics**

Demographic information and baseline characteristics will be described for all patients included in the study.

Past medical history and concomitant treatments will be described overall and per group.

The frequency of the previous medications will be calculated according to "patient" approach: the frequency will be calculated globally and by 'système organe classe' (SOC) and Preferred Term (PT) of the terminology used in the dictionary for regulatory activities (MedDRA).

The frequency of previous treatments will be presented in "patient" approach: the frequency of patients who received at least one concomitant medication and frequency of patients with at least one prior medication will be calculated. Frequencies will be calculated by term ATC (terminology WHO-DD). Each table will be sorted in a descending order of frequency of ATC terms.

### **7.3.2 Primary analyses**

The primary objective of the study is to evaluate overall treatment compliance after 3-months follow-up and to compare this compliance between the 2 study groups: the group of patients with additional nurse-led follow-up and the group without nurse-led follow-up.

As such, the cumulated dose (mg) of the oral targeted therapy over the 3-month study will be described for each of the groups: number of observed values, mean, standard deviation, median, lower quartile, upper quartile, minimum, maximum, two-sided 95% confidence interval of the mean.

The mean cumulated dose will be compared between groups by Student test, or Wilcoxon rank sum test in case of non-normal data and/or non-homogeneity of variance.

A complementary analysis using a Kaplan-Meier curve will also be performed on the principal criteria, to evaluate the time between start of treatment and the first dose modification or interruption of the oral Targeted therapy.

